COVER PAGE

DCP Protocol #: NWU2017-09-01

Local Protocol #: NCI 2017-09-01

PHASE I TRIAL OF ENDOXIFEN GEL VERSUS PLACEBO GEL IN WOMEN UNDERGOING BREAST SURGERY

Consortium Name: Northwestern Cancer Prevention Consortium

Organization Name: Name of Consortium Principal

Investigator:

[name]. [name]

Northwestern University

[name] [contact] [contact] E-mail: [contact]

Organization Name: Northwestern University
Protocol Principal [name].
Investigator and Protocol Chair: Professor of Surgery

[name]

[name] [contact] [contact] E-mail: [contact]

Organization: Memorial Sloan-Kettering Cancer Center

Investigator: [name].

Evelyn H. Lauder Breast Center

[name] [contact] [contact]

E-mail: [contact]

Organization: Cedars-Sinai Medical Center

Investigator: [name].

Saul and Joyce Brandman Breast Center in the Samuel Oschin

Cancer Center

[name]

[contact] [contact] E-mail: [contact]

Organization: Northwestern University
Statistician: [name].

[name]

[name]

[contact]

[contact]

Email: [contact]

IND Sponsor: NCI/Division of Cancer Prevention

IND#

Agent(s)/Supplier: National Cancer Institute
NCI Contract # HHSN2612201200035I
Protocol Template: Version 8.5 08/31/2016

Protocol Version Date: May 11, 2020

Protocol Revision or

Amendment # Version 6.5

SCHEMA

NWU2017-09-01: Phase I trial of endoxifen gel versus placebo gel in women undergoing breast surgery

Women scheduled for mastectomy¹

Screening Visit 1 – consent, baseline tests, BESS Q, skin photos

2:1 Randomization in Cohorts 1 and 2. All subjects in Cohort 3 will receive active agent without randomization.

A maximum of 38 subjects will be enrolled.

Cohort 1²: 10mg daily³ Endoxifen gel (8) vs. placebo gel (4) Cohort 2: 20mg daily⁴ Endoxifen gel (8) vs. placebo gel (4)

Cohort 3: 10mg⁵ Endoxifen gel (8)

Daily treatments to both breasts for 21-28 days⁶ Weekly phone calls for compliance and AE assessment

Study Visit 1: End of study treatment tests, BESS Q, skin photos Study Visit 2: Mastectomy procedure Study Visit 3: 7-14 day post-op visit Final phone call/email/text message at 60 days

Endpoints

- 1) Skin toxicity evaluation using CTCAE v 4
- 2) Drug concentration in breast tissue and blood
- 3) Breast tissue biomarkers of endoxifen effect

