13. STATISTICAL CONSIDERATIONS

13.1 Study Design/Description

We plan a randomized, double-blind, Phase I trial with a control arm and a treatment arm, with dose escalation from 10 mg ENX gel daily (5 mg per breast) to 20 mg daily (10 mg per breast). Dose-limiting toxicity is defined as the occurrence of Grade 2 or greater skin response for any of the CTCAE parameters listed in Table 1.

Cohorts 1 and 2 will be randomized 2:1 (ENX gel and placebo). Cohort 3 will consist only of actively treated subjects. We planned that the sample size may range up to 38, depending on the frequency of DLT, and how early in each cohort DLT was observed. After completion of Cohort 2 (with accrual of 12 subjects each in Cohort 1 and 2), we will now accrue 8 subjects in Cohort 3, with a final accrual of 32 subjects. All subjects who receive any study drug will be evaluable for the primary endpoint of dermal toxicity.

[figure not shown]
We choose a 2:1 randomized design with a placebo arm with each dose in *order to establish variability of measurements when no treatment is applied*, and yet to provide treatment to as many subjects as possible. Randomization is double blinded, and the gel used in the treatment and control groups has similar appearance, consistency, and chemical composition, except for the presence of ENX in the active gel. The study will employ intent to treat principles. Although formal statistical comparison will be limited by the small sample size (as can be the case for Phase I trials), the placebo group will be used to interpret subjective symptoms such as skin irritation or pruritis. Combining placebo groups will yield a total of n=8, thus providing standard error of the estimate of SD/sqrt(8) and 0.5/sqrt/(8).

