13.5 Secondary Objectives, Endpoints, Analysis Plans

Secondary objectives:

- 1) Comparison of breast tissue concentrations of ENX at each dose will be done using visualization, graphics and by providing appropriate confidence interval (CI).
- 2) Plasma concentrations of ENX at each dose (10 mg per day and 20 mg per day), will be reported as observed concentrations with appropriate CIs.
- 3-5) Relate to comparison of the plasma levels for steroid hormones, plasma estrogenic response proteins, and plasma coagulation parameters. To assess treatment-related changes, the 95%CI of the mean difference post-pre and a test of the central parameter = 0 will be provided as in the previous objective.
- 6) To assess tissue biologic response to ENX gel treatment. These will be compared as pre- and post-therapy values, to explore the potential therapeutic effects of the two doses of ENX: a) by IHC for Ki67, ER, and PR expression; b) by nanostring assays, using a panel of genes reported to change with ENX exposure. For both IHC and gene expression, values for "pre" and for "post" measurements will be subtracted from each other and CIs for the mean difference will be provided. A nonparametric test of the central parameter being zero will be performed.
- 7) To bank germline DNA for future pooled analyses of polymorphisms in tamoxifen metabolizing enzymes, statistical analysis will be used as needed (optional).
- 8) Analysis of symptoms as reported in the BESS questionnaire: This uses scores where the lowest describes "no symptom" and the highest reflects "extremely" or "always". The high scores are adverse. When subtracting post-pre measures, negative values suggest improvement over time, while positive suggest worsening. We will provide graphical displays of these differences as histograms with x-axis values -5, -4, ...0, ... 4, 5 and empirical mass function on the top. To compare the dose groups (low, high) and singular dose versus placebo, if appropriate, we will use the nonparametric two sample Wilcoxon-Mann-Whitney test, with corrections for ties. The study was not specifically powered for such analysis, and resulting one and two sided p-values will be considered descriptive statistics useful for future analyses. Average, median and range of scores for each noted group will be provided as descriptive measures of location and variance. We will use multiple imputation via non-parametric probability integral transformation[53] to impute missing data as appropriate.

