All tests will be two-sided. We will use multiple imputation via non-parametric probability integral transformation (Helenowski, PhD Dissertation, 2011) to impute missing data as appropriate.

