13.8 Evaluation of Response

All participants included in the study who received agent will be assessed for response to intervention, even if there are major protocol deviations.

All of the participants who met the eligibility criteria (with the exception of those who did not receive study agent) will be included in the main analysis. All conclusions regarding efficacy will be based on all eligible participants.

Sub-analyses may be performed on the subsets of participants, excluding those for whom major protocol deviations have been identified (e.g., early death due to other reasons, early discontinuation of intervention, major protocol violations, etc.). However, sub-analyses will not serve as the basis for drawing conclusions concerning efficacy, and the reasons for excluding participants from the analysis should be clearly reported. For all measurements of response, the 95% confidence intervals will be provided.

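### The BESS comparison in section 13.5, item 8 does not use the collected baseline score as a covariate; adjusting dose versus placebo for it would be a cheap, minor improvement

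*Combined protocol and SAP*

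**What the plan says.** Item 8 of section 13.5 sets the direction of the BESS difference: "When subtracting post-pre measures, negative values suggest improvement over time, while positive suggest worsening". It plans histograms of these differences and then moves to group comparisons, introduced by "To compare the dose groups (low, high) and singular dose versus placebo, if appropriate", for which "we will use the nonparametric two sample Wilcoxon-Mann-Whitney test, with corrections for ties". It never says outright that the test is run on the differences, but nothing else in the item is offered as the tested variable. No covariate for BESS appears anywhere in section 13.

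The item limits its own claims: "The study was not specifically powered for such analysis, and resulting one and two sided p-values will be considered descriptive statistics". It also plans the average, median and range of scores by group. The closing paragraph of section 13.5 adds "All tests will be two-sided", and section 13.8 says "For all measurements of response, the 95% confidence intervals will be provided". Item 8 itself lists no interval for BESS.

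On group sizes, the schema gives each randomized cohort as "Endoxifen gel (8) vs. placebo gel (4"). Section 13.1 pools the two placebo groups to 8. Cohort 3 adds 8 women on 10 mg daily without randomization. Item 8 does not say which of these groups enter the test. BESS is scheduled at Screening Visit 1 and Study Visit 1 (sections 7.1, 7.2.1 and 7.4.1), so the baseline score is available.

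**The concern.** A change score subtracts the whole baseline value, noise included. If pre- and post-treatment scores are imperfectly correlated, a group that happens to start with worse symptoms will tend to show improvement, and a group that starts better will tend to show worsening. In groups this small, chance baseline differences are not negligible. Using baseline as a covariate removes only as much of the baseline difference as the data support, and usually leaves a less variable treatment contrast.

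At stake is the quality of the symptom comparison behind objective 1.2.8 and hypothesis 8 in section 2.3.1. The plan wants these results to be useful for later analyses. No dose, stopping or efficacy decision depends on them.

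**Working it through.** **The plan's own figures.** Pooled placebo is 4 + 4 = 8, so the standard error in section 13.1 is SD/√8 = 0.354 SD, and 0.5/√8 = 0.177 for a proportion. Accrual is 12 + 12 + 8 = 32. All agree with the text. The plan gives no sample size or power figure for BESS.

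**Inputs.** From the documents: 8 women per randomized active group, and 4 placebo per cohort (8 pooled). Assumed: equal SD before and after treatment, a pre-post correlation r shown as a range, and a two-sided 0.05 level. N is the total number in the comparison.

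**Chance baseline difference.** Its SD is SD × √(1/n₁ + 1/n₂). For 8 v 8 this is √(1/8 + 1/8) = 0.50 SD. A difference larger than 0.5 SD has probability 2 × (1 − Φ(1)) = 0.317.

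**Shift of the change contrast.** Given a baseline difference D, the change contrast is expected to move by (1 − r) × D in the opposite direction. Its standard error at 8 v 8 is √(2(1 − r)) × 0.5 SD.

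**Precision.** The variance of the change contrast is proportional to 2(1 − r). That of the linear baseline-adjusted contrast is proportional to (1 − r²) × [1 + 1/(N − 4)]. The ratio of adjusted to change is (1 + r)/2 × [1 + 1/(N − 4)]. With N = 16 the bracket is 13/12.

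| r | shift at D = 0.5 SD | shift ÷ SE | variance ratio (adjusted/change) | change in variance |
|---|---|---|---|---|
| 0.3 | 0.35 SD | 0.59 | 0.704 | −30% |
| 0.5 | 0.25 SD | 0.50 | 0.812 | −19% |
| 0.7 | 0.15 SD | 0.39 | 0.921 | −8% |
| 0.8 | 0.10 SD | 0.32 | 0.975 | −2.5% |
| 0.9 | 0.05 SD | 0.22 | 1.029 | +3% |

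**Break-even.** Setting the ratio to 1 gives r = 2/[1 + 1/(N − 4)] − 1.
- 8 v 8: 24/13 − 1 = 0.846.
- 8 v 4 (placebo from the same cohort only): 2/1.125 − 1 = 0.778. The baseline-difference SD rises to √(1/8 + 1/4) = 0.61 SD.
- 16 v 8 (Cohort 3 added): 2/1.05 − 1 = 0.905. The baseline-difference SD falls to √(1/16 + 1/8) = 0.43 SD.

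**Check with rank methods.** Simulation at 8 v 8 with 4,000 replicates per setting compared Wilcoxon-Mann-Whitney on change with Quade's rank analysis of covariance.
- No effect, all replicates: the change test rejected in 3.8% to 4.4% with normal scores. On a 0–4 item with half of baseline scores at 0, it rejected in 3.4% and 4.7% at r = 0.5 and 0.7.
- No effect, only replicates with an imbalance above 0.5 SD (about a third): 8.4%, 7.0% and 5.4% at r = 0.3, 0.5 and 0.7 with normal scores; 5.9% and 7.6% on the 0–4 item at r = 0.5 and 0.7.
- Assumed 1-SD effect, power of the change test v rank adjustment: 28% v 44% (r = 0.3), 38% v 50% (0.5), 58% v 62% (0.7) and 88% v 82% (0.85). On the 0–4 item: 39% v 47% (0.5) and 54% v 56% (0.7).

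With normal scores and no effect, the rank-adjusted test rejected in 4.8% to 6.0%. Part of its power advantage is therefore a difference in size rather than efficiency.

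**The case against.** The strongest reply is that the plan has already put this analysis in its place: unpowered, conditional on being appropriate, with p-values treated as description. Section 13.1 also concedes that small numbers limit formal comparison. That stands, and it is why the point is minor. It does not remove the gain, since a descriptive contrast is more useful when it is less affected by where the groups happened to start.

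A reader might infer that the planned test is biased or invalid. The documents do not support that. Under randomization the expected baseline difference is zero and the overall error rate holds. The shifts in the table are conditional on a realized imbalance, and even then the simulated error was about 5% to 8%.

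A reader might also infer that precision is certainly lost. It is not: the result depends on a correlation that the documents do not give, and at high correlation the change score is the better choice. The variance figures are for linear models, and the rank simulation supports the same direction only up to r = 0.7.

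Two further objections stand. The low v high dose comparison sets sequential cohorts against each other (section 3.2.1), so imbalance there is not only chance. Eight placebo women require pooling across cohorts, which the item does not specify. The floor at 0 on the Appendix D items adds little to the case: a woman at 0 can still worsen, which is the safety concern, and a linear baseline term does not remove a floor.

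**Conclusion.** The point holds as a cheap, minor improvement. On its natural reading, item 8 tests raw changes and makes no further use of the baseline score. For 8 active v 8 pooled placebo, an imbalance of one SD of its chance distribution moves the contrast by 0.39 to 0.59 of its standard error across r = 0.7 to 0.3, and adjustment would reduce variance by 8% to 30% over that range. The advantage is nearly gone at 0.8 and reverses above about 0.85, or above about 0.78 at 8 v 4.

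This rests on an assumed correlation, equal SDs before and after treatment, and pooled placebo women who are comparable across the two cohorts.

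It would be tempting to say that hypothesis 8 stands or falls on this test. It does not. The item also provides histograms and summaries, and the weekly calls in section 7.3.1 ask about hot flashes, vaginal discharge and bleeding. Neither the planned p-value nor an adjusted one can show that symptoms are similar at these sample sizes.

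**What to change.** In item 8 of section 13.5:
- Name the tested variable and the groups: which placebo women are used, and whether Cohort 3 is included.
- For dose versus placebo, compare post-treatment BESS adjusted for baseline BESS, by Quade's rank analysis of covariance or by a linear model with group and baseline and a two-sided permutation p-value.
- Report the adjusted difference with a 95% CI. If Quade's method supplies the p-value, take the estimate and interval from the linear model.
- Keep the change histograms and group summaries as description.
- Label low v high dose as a non-randomized comparison of sequential cohorts.
- Keep the statement that the analysis is descriptive, and do not read a large p-value as evidence of similarity.

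The cost is a few lines of SAP text and code, with no new data. The price in the analysis is one degree of freedom, and a slight loss of precision if the pre-post correlation proves very high.

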13.6 Reporting and Exclusions

Compliance is defined as consumption of 80% of the prescribed dose over the whole study period, and of all of the last 3 required doses. Where information is available, data on non-compliant patients will be considered for dose-response analysis. Missing data will be treated via multiple imputations as described in previous sections.

13.7 Evaluation of Toxicity

All participants will be evaluated for toxicity as described in the protocol. Dose-Limiting Toxicity (DLT) is defined as Grade 2 or greater skin toxicity, using CTCAE criteria for the parameters shown in Table 1. The Grade 2 or greater reaction should occur at the application site for 48 hours or longer and be definitely, probably, or possibly related to the study drug.

13.8 Evaluation of Response

All participants included in the study who received agent will be assessed for response to intervention, even if there are major protocol deviations.

All of the participants who met the eligibility criteria (with the exception of those who did not receive study agent) will be included in the main analysis. All conclusions regarding efficacy will be based on all eligible participants.

Sub-analyses may be performed on the subsets of participants, excluding those for whom major protocol deviations have been identified (e.g., early death due to other reasons, early discontinuation of intervention, major protocol violations, etc.). However, sub-analyses will not serve as the basis for drawing conclusions concerning efficacy, and the reasons for excluding participants from the analysis should be clearly reported. For all measurements of response, the 95% confidence intervals will be provided.

13.9 Interim Analysis

Interim analyses and stopping rules are those inherent in toxicity evaluation and dose escalation / deescalation. Early termination may occur if the lowest dose is found toxic.

13.10 Ancillary Studies

Ancillary studies will be performed as needed and as possible. Power analyses have not been performed for the present time lack of knowledge of parameters and effect sizes involved. Bonferroni correction for multiple comparisons will be applied as possible in given context.

14. ETHICAL AND REGULATORY CONSIDERATIONS

14.1 Form FDA 1572

Prior to initiating this study, the Protocol Lead Investigator at the Lead or Participating Organization(s) will provide a signed Form FDA 1572 stating that the study will be conducted in compliance with regulations for clinical investigations and listing the investigators, at each site that will participate in the protocol. All personnel directly involved in the performance of procedures required by the protocol and the collection of data should be listed on Form FDA 1572.

14.2 Other Required Documents

- 14.2.1 Current (within two years) CV or biosketch for all study personnel listed on the Form FDA 1572 and Delegation of Tasks form for the Lead Organization and all Participating Organizations. CVs or biosketches do not need to be updated for participating study staff after drug shipment authorization (DSA).
- 14.2.2 Current medical licenses (where applicable) for all study personnel listed on Form FDA 1572 and Delegation of Tasks form for the Lead Organization and all Participating Organizations.
- 14.2.3 Lab certification (e.g., CLIA, CAP) and lab normal ranges for all labs listed on Form FDA 1572 for the Lead Organization and all Participating Organizations.
- 14.2.4 Documentation of Good Clinical Practice training for all study personnel listed on the FDA Form 1572 and Delegation of Tasks form for the Lead Organization and all Participating Organizations.
- 14.2.5 Documentation of Federalwide Assurance (FWA) number for the Lead Organization and all Participating Organizations.
- 14.2.6 Signed Investigator's Brochure/Package Insert acknowledgement form
- 14.2.7 Delegation of Tasks form for the Lead Organization and all Participating Organizations signed by the Principal Investigator for each site and initialed by all study personnel listed on the form
- 14.2.8 Signed and dated NCI, DCP Financial Disclosure Form for all study personnel listed on Form FDA 1572 for the Lead Organization and all Participating Organizations

14.3 Institutional Review Board Approval

Prior to initiating the study and receiving agent, the Investigators at the Lead Organization and the Participating Organization(s) must obtain written approval to conduct the study from the appropriate IRB. Should changes to the study become necessary, protocol amendments will be submitted to the DCP PIO according to DCP Amendment Guidelines. The DCP-approved amended protocol must be approved by the IRB prior to implementation

14.4 Informed Consent

All potential study participants will be given a copy of the IRB-approved Informed Consent to review. The investigator will explain all aspects of the study in lay language and answer all questions regarding the study. If the participant decides to participate in the study, he/she will be asked to sign and date the Informed Consent document. The study agent(s) will not be released to a participant who has not signed the Informed Consent document. Subjects who refuse to participate or who withdraw from the study will be treated without prejudice.

Participants must be provided the option to allow the use of blood samples, other body fluids, and tissues obtained during testing, operative procedures, or other standard medical practices for further research purposes. If applicable, statement of this option may be included within the informed consent document or may be provided as an addendum to the consent. A Model Consent Form for Use of Tissue for Research is available through a link in the DCP website.

Prior to study initiation, the informed consent document must be reviewed and approved by NCI, DCP, the Consortium Lead Organization, and the IRB at each Organization at which the protocol will be

implemented. Any subsequent changes to the informed consent must be approved by NCI, DCP, the Consortium Lead Organization's IRB, and then submitted to each organization's IRB for approval prior to initiation.

14.6 Other

This trial will be conducted in compliance with the protocol, Good Clinical Practice (GCP), and the applicable regulatory requirements.


APPENDIX A Performance Status Criteria

ECOG Performance Status Scale

Grade	Descriptions
0	Normal activity. Fully active, able to
	carry on all pre-disease performance
	without restriction.
1	Symptoms, but ambulatory. Restricted in
	physically strenuous activity, but
	ambulatory and able to carry out work of
	a light or sedentary nature (e.g., light
	housework, office work).
2	In bed <50% of the time. Ambulatory and
	capable of all self-care, but unable to
	carry out any work activities. Up and
	about more than 50% of waking hours.
3	In bed >50% of the time. Capable of only
	limited self-care, confined to bed or chair
	more than 50% of waking hours.
4	100% bedridden. Completely disabled.
	Cannot carry on any self-care. Totally
	confined to bed or chair.
5	Dead.

Karnofsky Performance Scale

Percent	Description
100	Normal, no complaints, no evidence of
	disease.
90	Able to carry on normal activity; minor
	signs or symptoms of disease.
80	Normal activity with effort; some signs
	or symptoms of disease.
70	Cares for self, unable to carry on
	normal activity or to do active work.
60	Requires occasional assistance, but is
	able to care for most of his/her needs.
50	Requires considerable assistance and
	frequent medical care.
40	Disabled, requires special care and
	assistance.
30	Severely disabled, hospitalization
	indicated. Death not imminent.
20	Very sick, hospitalization indicated.
	Death not imminent.
10	Moribund, fatal processes progressing
	rapidly.
0	Dead.

